9.5.2.2 Description of Procedures/Assessments Schedule

Please refer to [Table 4](#) and [Table 5](#) for the timings of the procedures and assessments to be performed during the study. Screening assessments will be organized into 5 tiers (see [Table 4](#)). See [Section 9.5.1](#) for a full description of the procedures and assessments to be performed during this study.

[Table 6](#) presents the number of blood and CSF samples, and the estimated total volume of blood and CSF that will be collected throughout the study. (revised per Amendment 02) Additional samples may be taken at the discretion of the investigator if the results of any tests fall outside reference ranges or if clinical symptoms necessitate testing to ensure subject safety. Actual specimen volumes may vary based on local regulations. (revised per Amendment 02)

Table 6 Summary of Estimated Blood and CSF Sample Volumes

Assessment	Total Number of Collection Time Points	Sample Volume, Number of Time Points × Volume per Collection (mL)			Total Volume ^a (mL)
		Screening Visits	Visit 2 Baseline (predose) (revised per Amendment 03)	Treatment and Follow-Up Periods	
Blood					
Clinical chemistry (revised per Amendments 02 and 03)	15	1×2.5 mL	1×2.5 mL	13×2.5 mL	37.5 mL
Serum pregnancy test at Screening (females of child-bearing potential only)	0	can use blood drawn for clinical chemistry	can use blood drawn for clinical chemistry	none	no additional volume
Hematology (revised per Amendment 03)	15	1×2 mL	1×2 mL	13×2 mL	30 mL
Coagulation (revised per Amendments 02 and 03)	15	1×1.8 mL	1×1.8 mL	13×1.8 mL	27 mL
Thyroid function tests (thyroid stimulating hormone, free triiodothyronine and free thyroxine)	1	1×5 mL	none	none	5 mL
Viral screen at Screening (Hepatitis B and C) (revised per Amendment 02)	1	1×2.5 mL	none	none	2.5 mL
Viral characterization at Visit 2 (previous exposure to CMV, HSV1, HSV2, etc.) (revised per Amendments 02 and 03)	1	none	1×3.5 mL	none	3.5 mL

Table 6 Summary of Estimated Blood and CSF Sample Volumes

Assessment	Total Number of Collection Time Points	Sample Volume, Number of Time Points × Volume per Collection (mL)			Total Volume ^a (mL)
		Screening Visits	Visit 2 Baseline (predose) (revised per Amendment 03)	Treatment and Follow-Up Periods	
Vitamin B12 at Screening and MMA where available (revised per Amendments 02, 03, and 05)	0	can use blood drawn for TFT	none	none	no additional volume
Blood for immunologic assessments, (revised per Amendments 03 and 05) ^b	8		1×10 mL	7×10 mL	80 mL
Blood for PBMCs (revised per Amendment 05)	4	none	1×10 mL	3×10 mL	40 mL
Blood for immune status (revised per Amendment 03)	8	none	1×5 mL	7×5 mL	40 mL
AD diagnostics and exploratory biomarker (revised per Amendment 03)	1	1×6 mL	none	none	6 mL
PD and exploratory biomarker sample (revised per Amendments 01, 02, and 03)	10	none	1×12 mL	9×6 mL	66 mL
PK analysis (revised per Amendment 02)	7	none	none	14×2 mL	28 mL
Pharmacogenomic sample (revised per Amendments 01 and 02)	1	1×6 mL	none	none	6 mL
All blood samples, total volume collected (revised per Amendments 01, 02, 03, and 05)		25.8 mL	46.8 mL	298.9 mL	371.5 mL
CSF					
Amyloid eligibility	1	1×12 mL	none	none	12 mL
PD / PK (optional longitudinal substudy)	1	none	none	1×12 mL	12 mL

Note: Actual volumes may be less, based on regional differences in Central Laboratories.

AD = Alzheimer's disease, CMV = cytomegalovirus, CSF = cerebrospinal fluid, HSV1 = herpes simplex virus 1 (orolabial herpes), HSV2 = herpes simplex virus 2 (genital herpes), PBMCs = peripheral blood mononuclear cells, PD = pharmacodynamics, PK = pharmacokinetic, TFT = thyroid function Test.

a: The total volume includes all blood/CSF collection from Screening through Week 117 (Follow-up Visit) ; actual volume may vary based on local regulations. (revised per Amendment 02)

b: Immunological assessment samples not required for subjects randomized after 07 Sep 2018 - reducing total blood volume to 291.5 mL (revised per Amendment 05)

9.5.3 Appropriateness of Measurements

All clinical assessments are standard measurements commonly used in studies of AD.

Standard safety assessments incorporated into this protocol include assessment of AEs and SAEs, measurement of vital signs, clinical laboratory assessments, physical examinations (including dermatologic review), neurologic examinations, ECG measurements, assessments of suicidal thinking and behavior, and MRI.

9.5.4 Reporting of Serious Adverse Events, Pregnancy, and Events Associated with Special Situations

9.5.4.1 Reporting of Serious Adverse Events

All SAEs, regardless of their relationship to study treatment, must be reported on a completed SAE form by email or fax as soon as possible but no later than 24 hours from when the investigator becomes aware of the event.

SAEs, regardless of causality assessment, must be collected up to 4 weeks after the last dose of study drug. All SAEs must be followed to resolution or, if resolution is unlikely, to stabilization. Any SAE judged by the investigator to be related to the study treatment or any protocol-required procedure should be reported to the sponsor regardless of the length of time that has passed since study completion. (revised per Amendment 05)

The detailed contact information for reporting of SAEs is provided in the Investigator Study File.

For urgent safety issues, please ensure all appropriate medical care is administered to the subject and contact the appropriate study team member listed in the Investigator Study File.

It is very important that the SAE report form be filled out as completely as possible at the time of the initial report. This includes the investigator's assessment of causality.

Any follow-up information received on SAEs should be forwarded within 1 business day of its receipt. If the follow-up information changes the investigator's assessment of causality, this should also be noted on the follow-up SAE form.

Preliminary SAE reports should be followed as soon as possible by detailed descriptions including copies of hospital case reports, autopsy reports, and other documents requested by the sponsor.

The investigator must notify his/her IRB/IEC of the occurrence of the SAE in writing, if required by their institution. A copy of this communication must be forwarded to the sponsor, or its designee, to be filed in the sponsor's Trial Master File.

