9.5.1.5.2 SERIOUS ADVERSE EVENTS AND EVENTS ASSOCIATED WITH SPECIAL SITUATIONS

An SAE is any untoward medical occurrence that at any dose:

- Results in death
- Is life-threatening (ie, the subject was at immediate risk of death from the adverse event as it occurred; this does not include an event that, had it occurred in a more severe form or was allowed to continue, might have caused death)

- Requires inpatient hospitalization or prolongation of existing hospitalization
- Results in persistent or significant disability/incapacity
- Is a congenital anomaly/birth defect (in the child of a subject who was exposed to the study drug)

Other important medical events that may not be immediately life-threatening or result in death or hospitalization but, when based on appropriate medical judgment, may jeopardize the subject or may require intervention to prevent one of the outcomes in the definition of SAE listed above should also be considered SAEs. Medical and scientific judgment should be exercised in deciding whether expedited reporting is appropriate in such situations.

For this study, the following events should always be considered serious and reported as an important medical event even if it does not meet other serious criteria:

- Ocular herpes
- New onset seizures
- Symptomatic cerebral vasogenic edema

In addition to the above, events associated with special situations include pregnancy or exposure to study drug through breastfeeding; AEs associated with study drug overdose, misuse, abuse, or medication error. These events associated with special situations are to be captured using the SAE procedures but are to be considered as SAEs only if they meet 1 of the above criteria. All AEs associated with special situations are to be reported on the CRF whether or not they meet the criteria for SAEs.

All SAEs must be followed to resolution or, if resolution is unlikely, to stabilization.

The following hospitalizations are not considered to be SAEs because there is no “adverse event” (ie, there is no untoward medical occurrence) associated with the hospitalization:

- Hospitalizations for respite care
- Planned hospitalizations required by the protocol
- Hospitalization planned before informed consent (where the condition requiring the hospitalization has not changed after study drug administration)
- Hospitalization for administration of study drug or insertion of access for administration of study drug

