Day	1	15	29	57	85	183	274	365	456	547	638	729		757	813	
Week	1	3	5	9	13	27	40	53	66	79	92	105		109	117	
Weeks elapsed since 1st dose	0	2	4	8	12	26	39	52	65	78	91	104		108	116	
Nominal months elapsed since 1st dose	0		1	2	3	6	9	12	15	18	21	24		25	27	
Procedures/ Assessments																

- b: Subjects who discontinue taking study drug prematurely for any reason will undergo an ED Visit within 7 days of their last dose of study drug. In addition, Follow-up Visits will be scheduled 4 and 12 weeks after the last dose of study drug (Visit 14 and Visit 15, respectively). Subjects who discontinue study drug before reaching 12 months of treatment will also be asked to return to the clinic for a 12 month clinical assessment and then again at 24 months. Subjects who discontinue treatment between 12 and 24 months of treatment will be asked to return to the clinic for a 24 month clinical assessment. Subjects who discontinue early from study drug are considered “on study” as long as they continue to return for their clinical assessments at 12 and 24 months as outlined above, at which efficacy (MMSE, CDR, ADAS- cog14) and quality of life (EQ-5D, QOL-AD and Zarit’s Burden Interview) will be assessed along with concomitant medications. New AEs will be collected for 4 weeks post last dose and followed-up for 12 weeks, or until resolution, whichever comes first. If >4 weeks post last dose only AEs relating to study procedures will be collected. These 12 and 24 month clinical assessment visits do not need to be attended if they fall within 8 days (visit window) after the ED Visit or within ±8 days of either of the Follow-up Visits (Visit 14 and Visit 15).

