9.5.5 Completion/Discontinuation of Subjects

A subject may elect to withdraw from the study at any time for any reason. All subjects who discontinue study drug early for any reason will undergo an ED Visit within 7 days of their last dose of study drug (see [Section 9.1.2.2](#)). In addition, Follow-up Visits will be scheduled 4 and 12 weeks after the last dose of study drug (Visit 14 and Visit 15, respectively) (see [Section 9.1.2.2](#)). These Follow-up Visits will be conducted to monitor efficacy and safety parameters after early withdrawal from the study or discontinuation of study drug. See [Table 5](#) for full details of the assessments to be performed at these visits.

All subjects who discontinue study drug before reaching 12 months of treatment will also be asked to return to the clinic for a 12 month clinical assessment and then again at 24 months. Subjects who discontinued treatment between 12 and 24 months of treatment will be asked to return to the clinic for a 24-month clinical assessment. Subjects who discontinue early from study drug are considered “on study” as long as they continue to return for their clinical assessments at 12 and 24 months as outlined above, at which efficacy and quality of life will be assessed along with concomitant medications and AEs. However, subjects who discontinue study drug early are not considered to have ‘completed’ the study as a final Subject Disposition. A subject removed from the study for any reason may not be replaced.

The investigator will promptly explain to the subject involved that the study will be discontinued for that subject and provide appropriate medical treatment and other necessary measures for the subject. A subject who has ceased to return for visits will be followed up by mail, phone, or other means to gather information such as the reason for failure to return, the status of treatment compliance, the presence or absence of AEs, and clinical courses of signs and symptoms.

The primary reasons for early withdrawal from the study are: AE, lost to follow up, subject choice, withdrawal of consent, pregnancy, study terminated by sponsor, and other. The secondary reasons for early withdrawal from the study are: AE, subject choice, and other.

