9.7.1.3 Subject Disposition

The number of subjects screened, the number (percent) of subjects who failed screening, and the reasons for screen failure will be summarized, based on data reported on the Screening Disposition eCRF. The distribution of the number of randomized subjects enrolled by each site will be summarized for each randomized treatment group. The primary reasons for screen failures (did not meet inclusion or met exclusion criteria, AE, lost to follow-up, withdrawal of consent, and other) will be presented.

Study Completion: the number (percent) of randomized and treated subjects who completed the study and who discontinued from the study will be summarized according to the primary reason for discontinuation and secondary reason(s) for discontinuation, based on data reported on the Subject Disposition (Study Phase) CRF. The number (percent) will be presented by treatment group and total for subjects; randomized, not treated, treated, who completed the study, and discontinued from the study. The primary reasons for early withdrawal from the study are: AE, lost to follow-up, subject choice, withdrawal of consent, pregnancy, study terminated by sponsor, and other. The secondary reasons for early withdrawal from the study are: AE, subject choice, and other.

Completion of Study Treatment: the number (percent) of randomized and treated subjects who completed study drug and who discontinued from study drug will be summarized according to the primary reason for discontinuation and also according to secondary reason(s) for discontinuation, based on data reported on both the Subject Disposition (Study Phase) eCRF and ED from Study Drug eCRF. The number (percent) will be presented by treatment group and total for subjects; randomized, not treated, treated, who completed study drug, and discontinued from study drug. The primary reasons for early discontinuation from the study drug are: AE, subject choice, pregnancy, inadequate therapeutic effect, and other. The secondary reasons for early discontinuation from the study drug are: AE, subject choice, inadequate therapeutic effect, and other.

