9.7.1.6.1 PRIMARY EFFICACY ANALYSIS

The primary analysis will be based on an intent to treat philosophy without regard to adherence to treatment. The primary analysis of the change from baseline in CDR-SB at 24 months will be performed to compare elenbecestat 50 mg per day versus placebo using a linear mixed effects model for repeated measures (MMRM) on the FAS. The MMRM model will include fixed effects of treatment group, visit, treatment group by visit interaction, baseline CDR-SB, baseline CDR-SB by visit interaction, and randomization stratification variables (ie, region [7 levels], clinical dementia [yes, no], and concurrent AD medication use at randomization [Visit 2] [yes, no]). *ApoE4* status may be included in the model if appropriate. (revised per Amendment 05) An unstructured covariance matrix will be employed to model the covariance of within subject effect; if MMRM fails to converge then a covariance structure with fewer parameters from the following list will be employed according to the prespecified order in the list until the MMRM converges. The list of covariance structure will include Heterogeneous Toeplitz, Toeplitz, Heterogeneous Compound Symmetry, and Compound Symmetry. This primary analysis will include all observed post baseline data of the change from baseline in CDR-SB without imputation of missing values. The treatment effect for elenbecestat versus placebo will be compared at

24 months based on MMRM model. The LS means and difference in LS means between elenbecestat treatment group and placebo, and corresponding 95% CI will be presented.

The null hypothesis is that there is no difference in the mean change from baseline in CDR-SB at 24 months between elenbecestat 50 mg per day and placebo. The corresponding alternative hypothesis is that there is a difference in the mean change from baseline in CDR-SB at 24 months between elenbecestat 50 mg per day and placebo.

The primary analysis will be repeated to minimize the impact of change in concomitant AD medications where efficacy data after initiation of new AD medications and increase of current AD medications will be censored.

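### Complete all-cause mortality by randomized arm to month 24 is not secured: deaths judged unrelated, from events starting more than 4 weeks after the last dose, have no clear collection rule and no disposition category of their own

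*Protocol*

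**What the plan says.** On SAEs, Section 9.5.4.1 of the protocol sets the window: "SAEs, regardless of causality assessment, must be collected up to 4 weeks after the last dose of study drug". It makes two provisions beyond it. An SAE judged related to study treatment or to a protocol-required procedure "should be reported to the sponsor regardless of the length of time that has passed since study completion". And, for events already reported, "All SAEs must be followed to resolution or, if resolution is unlikely, to stabilization".

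On AEs after the window, Section 9.3.3 collects new events for 4 weeks after the last dose and then only those tied to study procedures. Table 5 footnote b says the same: "If >4 weeks post last dose only AEs relating to study procedures will be collected". Footnote ff repeats it.

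On follow-up, Section 9.3.3 keeps subjects who stop drug on study and recalls them at months 12 and 24. Section 9.7.1.6.1 explains why these visits matter: "The primary analysis will be based on an intent to treat philosophy without regard to adherence to treatment".

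Section 9.5.5 describes the same visits but includes AEs among what is assessed. It also has sites trace subjects who stop attending, to learn why and whether AEs occurred.

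On disposition, Section 9.5.5 gives the primary reasons for study withdrawal as "AE, lost to follow up, subject choice, withdrawal of consent, pregnancy, study terminated by sponsor, and other". Section 9.7.1.3 uses the same seven: "AE, lost to follow-up, subject choice, withdrawal of consent, pregnancy, study terminated by sponsor, and other".

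On outputs, Section 9.7.1.8.2 plans a summary by treatment group of TEAEs leading to death and a listing of all AEs leading to death.

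**The concern.** Efficacy follow-up runs by randomized arm to month 24, whereas all-cause SAE collection ends with drug exposure plus 4 weeks. If stopping differs between arms, the observation time for deaths differs too, and stopping is unlikely to be neutral. Under Section 9.3.3, confirmed lymphopenia occurring twice within 6 months, a severe infection that does not resolve, and certain rashes all lead to permanent discontinuation, and Section 7.1 links the drug to lower lymphocyte counts. The clock also starts at the last dose taken. A subject interrupted for 4 weeks and then stopped for good has used the whole window by the time of that decision.

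Reporting of late related SAEs does not replace a comparison by arm, because it depends on a causality judgement made case by case. In a population aged 50 to 85, a randomized comparison of all deaths is the safeguard against misattribution. A month-24 CDR-SB score missing because the subject died may also be indistinguishable from one missing through loss to follow-up.

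This is a data-collection rule. A statistical analysis plan cannot recover deaths that were never recorded.

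**Working it through.** **Setting the provisions side by side, for a subject who stopped drug and later died**

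| Situation | Governing text | Captured? |
|---|---|---|
| Event starts within 4 weeks of last dose, death in that time | 9.5.4.1 | Yes |
| Event starts within 4 weeks, death later | 9.5.4.1, SAEs followed to resolution or stabilization | Yes |
| Event starts after 4 weeks, judged related to drug or procedure | 9.5.4.1, no time limit | Yes |
| Event starts after 4 weeks, judged unrelated | 9.3.3 and Table 5 footnotes b and ff: not collected. 9.5.5: AEs assessed at months 12 and 24, non-attenders traced | Contradictory |

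Only the last row is open. A subject who has died attends neither visit, so even on the wording of Section 9.5.5 capture depends on tracing. If tracing reveals the death, Section 9.3.3 and Table 5 make no provision for recording an unrelated event. The withdrawal reason could be entered as AE or as other, but neither marks a death.

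**Size of the time outside the window (illustration)**

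The concern disputes no figure in the plan. The sample size was reproduced only to check the source of the total and the dropout rate. Inputs from Section 9.7.2: placebo mean change 1.46, 25% reduction, SD 2.05, two-sided alpha 0.05, power 90%, dropout 30%.

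- Difference: 0.25 × 1.46 = 0.365.
- Evaluable subjects by the normal formula: 663 per arm. Allowing for dropout: 663 / 0.70, rounded up, is 948 per arm, or 1896 in total. The t-test version gives 1898. The plan states 1900, so it reproduces.

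Total person-time to month 24 is 1900 × 2 = 3800 person-years, with no reduction for death or loss.

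Assume a share of subjects stops drug at times spread evenly over 0 to 2 years, and let w = 28 / 365.25 = 0.0767 years. The mean time outside the window per stopper, up to month 24, is (2 − w)² / (2 × 2) = 1.9233² / 4 = 0.925 years.

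| Assumed share stopping | Stoppers | Person-years outside | Share of 3800 |
|---|---|---|---|
| 15% | 285 | 264 | 6.9% |
| 30% | 570 | 527 | 13.9% |
| 40% | 760 | 703 | 18.5% |

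To put this in deaths a mortality rate must be assumed, since the protocol gives none. At 30% stopping and 0.5%, 1% or 2% per year in all subjects, about 3, 5 or 11 of about 19, 38 or 76 deaths fall in that time. These counts include related deaths and deaths from earlier events, which the protocol does capture, so the unsecured number is smaller at any given rate. They also pool two trials. At the minimum of 850 subjects in this study, 527 × 850 / 1900 = 236 person-years, or about 2 to 5 deaths at 1% to 2%.

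Completers are affected as well. All-cause collection ends about 4 weeks after the last dose, while Visit 15 is at 12 weeks and CDR-SB at 27 months is a secondary endpoint.

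**The case against.** The strongest defence is that the protocol provides more than Section 9.5.4.1 alone suggests. Several stronger readings are tempting, and the documents do not support them.

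- *Late deaths are not captured.* Not so in general. Related SAEs have no time limit, earlier SAEs are followed to their outcome, and Section 9.5.5 puts AEs into the off-drug visits and requires tracing. The supportable finding is a contradiction between sections and a residual gap.
- *Mortality cannot be compared by arm.* Deaths on treatment and within 4 weeks of it can be. In the illustration at 30%, about 86% of person-time lies inside the window.
- *TEAEs leading to death are the only planned mortality output.* Section 9.7.1.8.2 also plans a listing of all AEs leading to death, and its TEAE definition has no end date, so a late death recorded as an AE would enter the summary by arm. The limit lies in collection.
- *A death cannot be entered in disposition.* It can, as AE or other. It just cannot be told apart there.
- *The protocol expects lymphopenia to outlast the window.* The repeat counts after Visits 14 and 15 apply only if a low count is found. The reversal data in Section 7.1 show recovery between 6 and 21 days after the last of 14 daily doses.
- *30% is the rate of stopping drug.* It is a dropout allowance for the sample size. Some of those subjects leave the study, and no document gives the number who stop drug but remain followed.

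A 4-week SAE window is also a deliberate choice, with the passage marked as revised under Amendment 05, and how deaths enter the missing-data analyses is properly left to the statistical analysis plan. All of this stands, and it narrows the point. It leaves open the unrelated death from an event that starts late, because the protocol states no collection of vital status or all-cause death to month 24.

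**Conclusion.** The point holds in a limited form. The protocol does not secure a complete all-cause comparison of deaths by randomized arm to month 24. The gap is confined to deaths judged unrelated that arise from events starting more than 4 weeks after the last dose. Sections 9.3.3 and 9.5.5 and Table 5 give conflicting instructions on collecting such events, and the disposition reasons cannot single them out.

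Its true size is unknown. On the assumption of even stopping over 24 months, 7% to 18.5% of pooled person-time lies outside the window for 15% to 40% stopping, and part of that belongs to subjects who leave altogether. The expected number of deaths is small. The gap matters mainly if stopping differs by arm, which cannot be known in advance. It is worth closing because it is cheap to close.

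**What to change.** 1. Reconcile Section 9.5.5 with Section 9.3.3 and Table 5 footnotes b and ff on what is collected at the off-drug visits at months 12 and 24.
2. In Section 9.5.4.1 and Table 5 footnotes b and ff, require date and cause of death for every randomized subject to month 24 or Visit 15, whichever is later, whatever the causality and time since last dose, as far as consent allows.
3. Add death to the study-withdrawal reasons in Sections 9.5.5 and 9.7.1.3.
4. Report all-cause deaths by randomized arm, alongside the planned summary of TEAEs leading to death.

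The cost is one eCRF field, short changes of wording, and a little more site follow-up for subjects who do not return. The month 12 and 24 contacts are already planned, and the SAE window for other events can stay as it is.
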